#### 6.2.2 Safety Endpoint

Adverse events

See “5. Adverse Events Assessment and Reporting.”

[Rationale for the choice of secondary endpoint (efficacy endpoints)]

To assess the study drug’s safety by comparing the occurrences of adverse events between the steroid group and the placebo group.

#### 6.3 Exploratory Endpoints

Blood test (CRP, white blood cell count, hemoglobin, platelet count, blood glucose)

To investigate changes in the results of the blood tests (CRP, white blood cell count, hemoglobin, platelet count, blood glucose) between the most recent data on or before Day 0 and the most recent data on or after Day 7.

[Rationale for the choice of exploratory endpoint]

Several potential causes including anemia, psychologic problems, and cytokines have been proposed for the fatigue in terminal-stage cancer patients, but the causes are yet to be elucidated. Comparing CRP, white blood cell count, hemoglobin, platelet count, and blood glucose between the intervention group and the placebo group may provide data that indicate what the causes of fatigue might be.

## 7 Statistics

### 7.1 Approach in Analysis of Primary Endpoint

The approach in the analysis of the primary endpoint is to be specified in the statistical analysis plan prepared by a biostatistician before data lock.

The approach in the analysis of endpoints is as follows. The EORTC QLQ-C15-PAL fatigue (FA) subscale, the primary endpoint, will be scored from 0 to 100 in accordance with the scoring algorithm formulated by EORTC; differences between the two groups at baseline and one week post-treatment will be determined; and tests of differences will be carried out. The null-hypothesis is defined as “no difference in change of QLQ-C15-PAL fatigue (FA) score between the steroid-treated group and the placebo group.”

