### 0.4 Endpoints

#### 0.4.1 Primary endpoint

The FA (fatigue) score in EORTC QLQ-C15-PAL

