#### 4.2 Target Sample Size and Trial Period

- (1) Target sample size: 210 patients (corticosteroid group, 105; placebo group, 105)
- (2) Trial period, planned: June 17, 2014 (after ethics committee approval) to June 16, 2019

[Rationale for the choice of sample size]

Our earlier study in palliative care patients showed that the change in the fatigue (FA) scale on the

Quality of Life Questionnaire - Core 15 Palliative (QLQ-C15-PAL) was -15.3 in the group of patients whose answer was "better" and 0.0 in those whose answer was either "no change" or "worse." Assuming an intergroup difference of -15.5 for the detected change, the standard deviation for the change was 30.2, thus giving an effective size of 0.51. To detect an intergroup difference of 0.5 SD at a two-sided significance level of 5% and a statistical power of  $\geq 90\%$ , 168 patients in two groups (84 patients per group) are needed. Assuming a patient dropout rate of 20% during the trial, 210 patients in two groups (105 patients per group) are to be enrolled.

The assumption of a patient dropout rate of 20% during the trial is based on the following factors, which are unique to terminal-stage patients.

- 1) The QOL questionnaire is a survey form self-administered by patients. As cancer symptoms progress, some patients may not be able to self-administer the questionnaire a week after study commencement.
- 2) As the survey respondents are terminal-stage cancer patients, some of them may die.
- 3) Pain therapy and cancer progression may lower cognitive level.
- 4) Some of the patients may switch to home care during the end-stage of their lives.
- 5) Some of the end-stage patients may transfer to a hospital facility near their home for the remaining part of their lives.

[Rationale for the choice of trial period]

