## 6 Endpoints

### 6.1 Primary Endpoints

Fatigue (FA) score of EORTC QLQ-C15-PAL

The primary endpoint selected is the fatigue (FA) score, which represents a participant's QOL, on the EORTC QLQ-C15-PAL used to evaluate QOL on Day 7 after study commencement.

[Rationale for the choice of primary endpoint]

In the present trial, the subscale fatigue (FA) score as part of the assessment of patient QOL is considered the representative parameter of QOL and selected as the primary endpoint.

Palliative medicine is an approach aimed at improving QOL in patients and their families facing the issues related to a life-threatening disease. PS2/3 terminal-stage patients with advanced cancer-related fatigue who participate in the present trial share the treatment goal of QOL improvement. Thus, the QOL in participants will be assessed, with the score serving as an endpoint for assessing the efficacy of palliative medicine. The QOL questionnaire, however, is based on a multi-dimensional scale. The subscale fatigue (FA) has the greatest effect on QOL and is considered a representative parameter.

To reduce the load from EORTC on the patients receiving palliative care, the number of questions has been reduced from 30 in the EORTC QLQ-C30 used routinely to assess QOL in cancer patients to 15 in the disease-specific EORTC QLQ-C15-PAL for palliative care patients used to assess QOL in the present trial. Its Japanese version has been validated, with the validation results published. Registration with EORTC will take place before use.

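### The protocol gives the primary variable as Day 7 fatigue in 6.1 but as change from baseline in 7.1 and 4.2; one baseline-adjusted analysis would reconcile them

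*Protocol*

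**What the plan says.** - Section 0.4.1 gives the primary endpoint as "The FA (fatigue) score in EORTC QLQ-C15-PAL", with no time point and no mention of change.
- Section 6.1 ties the endpoint to the questionnaire "used to evaluate QOL on Day 7 after study commencement". It does not mention change.
- Section 7.1 leaves the approach to the primary analysis to a later document: it "is to be specified in the statistical analysis plan prepared by a biostatistician before data lock". The same section then describes an approach: "differences between the two groups at baseline and one week post-treatment will be determined; and tests of differences will be carried out". It sets the null hypothesis as "no difference in change of QLQ-C15-PAL fatigue (FA) score between the steroid-treated group and the placebo group".
- Section 4.2 derives the sample size from change: "Assuming an intergroup difference of -15.5 for the detected change, the standard deviation for the change was 30.2, thus giving an effective size of 0.51". It then sizes for 0.5 SD at a two-sided 5% level with at least 90% power. This gives 84 evaluable patients per group, and 105 per group enrolled after 20% dropout.
- The schedule in 4.15 places the QOL assessment at baseline (Day 0) and at Day 7 or discontinuation, so baseline FA is already collected.
- The protocol names no covariate for the primary comparison and excludes none.

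**The concern.** The section that defines the endpoint and the section that states the hypothesis use different variables. A t-test on Day 7 scores and a t-test on change scores can give different p-values on the same data. Whichever the SAP adopts, it departs from the wording of one protocol section, and the choice may be made as late as just before data lock. For a primary result, that leaves room to question whether the variable was fixed in advance.

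The sentence in 7.1 adds a second ambiguity. It may mean that the baseline-to-week-one difference is compared between arms, or that the arms are compared at each of the two times. The second reading includes a significance test at baseline, which tells nothing useful in a randomised trial.

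The power statement is also at stake, because it was derived for only one of the two variables.

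**Working it through.** **Inputs.** From 4.2: SD of change 30.2, design difference 0.5 SD, two-sided 5%, 84 per arm, 20% dropout. From 4.6.3: 1:1 allocation. Assumed, because the protocol does not give them: the correlation r between baseline and Day 7 FA, taken as 0.3 to 0.7, and the ratio of the baseline SD to the Day 7 SD, taken first as 1. All power figures use the normal approximation.

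**1. Reproduce the plan's figure.** n per arm = 2(1.960 + 1.282)² / 0.5² = 84.06. Power at 84 per arm: the design difference is 0.5 × 30.2 = 15.1 and the standard error is 30.2 × √(2/84) = 4.66. Then z = 15.1/4.66 = 3.24, and power = Φ(3.24 − 1.96) = 90.0% (89.6% by the t-test). Enrolment: 168/0.80 = 210. The stated sizes reproduce, and they belong to the change score. Section 4.2 quotes both −15.3 and −15.5, and both ratios to 30.2 round to 0.51. The size was computed on 0.5 SD, so that discrepancy does not affect it.

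**2. Unadjusted Day 7 score.** With equal SDs, Var(change) = 2 × SD² × (1 − r), so the Day 7 SD is 30.2/√(2(1 − r)). Power uses the same difference of 15.1 and 84 per arm.

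**3. ANCOVA with baseline FA.** The residual variance is SD² × (1 − r²). Divided by 2 × SD² × (1 − r), this gives a ratio to the change-score variance of (1 + r)/2.

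| r (assumed) | Power, change | Day 7 SD | Power, Day 7 unadjusted | ANCOVA residual SD | Variance ratio, ANCOVA to change | Power, ANCOVA |
|---|---|---|---|---|---|---|
| 0.3 | 90.0% | 25.5 | 97.0% | 24.3 | 0.65 | 98.0% |
| 0.5 | 90.0% | 30.2 | 90.0% | 26.2 | 0.75 | 96.3% |
| 0.7 | 90.0% | 39.0 | 70.9% | 27.8 | 0.85 | 94.0% |

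The two unadjusted analyses agree only at r = 0.5.

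**4. Unequal SDs.** In general, Var(change) − Var(ANCOVA) = (SD_baseline − r × SD_Day7)². This is never negative, but it can be zero. Inclusion criterion (4) selects on a high baseline fatigue response, which may narrow the baseline spread. With k = SD_baseline/SD_Day7 = 0.7 (assumed), the variance ratio is (1 − r²)/(k² + 1 − 2kr):

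- r = 0.3: 0.91/1.07 = 0.85, power 94.0%
- r = 0.5: 0.75/0.79 = 0.95, power 91.4%
- r = 0.7: 0.51/0.51 = 1.00, power 90.0%, so no gain

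**5. Why ANCOVA settles the wording.** Replacing Day 7 FA by change subtracts baseline FA from the outcome. With baseline FA in the model, this only lowers its coefficient by 1. The treatment estimate, its standard error and its p-value are identical for either outcome.

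**The case against.** The strongest reply is that this is SAP territory. Section 7.1 says so at the outset, and model form and covariates are commonly left there. Section 6.1 can be read as saying only what is measured and when, with 7.1 saying how it is compared. The single hypothesis in the protocol is on change, the sample size is on change, and the study hypothesis in 2.2 speaks of alleviation, which fits change. On that view, 6.1 is only loosely worded.

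Much of this stands, and it rules out several stronger readings that a reader might infer:

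- **That the protocol rejects baseline adjustment.** It does not. It is silent on covariates, and a change score already uses baseline.
- **That the trial is underpowered or wastes patients.** It reaches about 90% for the change score, as planned.
- **That selection on high baseline fatigue biases the result through regression to the mean.** It is expected equally in both randomised arms. Chance baseline imbalance affects precision, not validity.
- **That testing at baseline is planned.** This is one of two readings, and the null hypothesis that follows, on change alone, favours the other.
- **That ANCOVA brings a known gain.** Its size depends on a correlation and an SD ratio that the protocol does not give.

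The reply does not remove the mismatch. Despite deferring the method, 7.1 goes on to fix a null hypothesis on a variable other than the one that 6.1 defines. Stating the primary variable consistently is the protocol's own task.

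**Conclusion.** The point holds as an inconsistency in the definition of the primary variable, worth correcting before data lock. The intended treatment effect is the same under either variable; the standard error, the p-value and the power differ. The stated power carries over to an unadjusted Day 7 comparison only at a correlation near 0.5 under equal SDs. Over assumed correlations of 0.3 to 0.7, that comparison has between about 97% and 71% power.

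Baseline-adjusted ANCOVA is recommended because it makes the choice of variable immaterial and, in large samples, is never less precise than the change score. Under equal SDs its power is about 98% to 94% over the same range. The gain is smaller, and can vanish, if the baseline SD is narrower than the Day 7 SD. The inconsistency itself rests on the text alone; only the power comparisons need the assumed correlation and SD ratio.

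**What to change.** In 6.1 and 7.1, name one primary variable: change in FA from baseline to Day 7 or, equivalently under this model, FA at Day 7. Suggested wording for 7.1:

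*The primary analysis compares the arms on the change in FA from baseline to Day 7 by ANCOVA, with treatment and baseline FA in the model. The null hypothesis is that the adjusted mean difference between arms is zero. The adjusted difference, its 95% confidence interval and the two-sided p-value are the primary result. Baseline values are summarised by arm without significance tests.*

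Use the same variable and time point in 6.1 and 0.4.1, and carry the text into the SAP before data lock. The sample size can stay as it is.

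The cost is a few sentences and no extra patients or data. It is still a protocol revision, which 14.1 requires to be filed under the IRB procedure at each site; 4.2 counts 24 sites.

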### 7.2 Analysis Sets

Analysis sets are defined below. Details on handling of cases and procedures for handling missing and excluded cases and abnormal data are provided in the statistical analysis plan prepared before data lock. The efficacy endpoint analyses are to be performed on the full analysis set (FAS) and, for reference purpose, on the per protocol set as well. The safety endpoint analysis is to be performed on the safety analysis set.

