### 6.2 Secondary Endpoints

#### 6.2.1 Efficacy Endpoints

(1) QOL-related scores other than the FA score on EORTC QLQ-C15-PAL

The efficacy of the steroid is confirmed if the EORTC QLQ-C15-PAL subscales of physical functioning, emotional functioning, appetite loss, and overall QOL showed improvements on Day 7 after study commencement.

(2) NRS (numeric rating scale)

The efficacy is confirmed if the fatigue NRS on Day 7 after study commencement showed an improvement.

(3) Survival time

Assess time to death with the day of enrollment (randomization) as the starting point. The efficacy is confirmed if the survival time is extended.

[Rationales for the choices of secondary endpoints (efficacy endpoints)]

(1) To assess improvements in the EORTC QLQ-C15-PAL subscales of physical functioning, emotional functioning, appetite loss, and overall QOL that are related to fatigue, in addition to the

fatigue subscale.

(2) To use the fatigue NRS, which is used by NCCN for screening fatigue, as one of the efficacy endpoints in the present trial.

(3) To ascertain in this 1-week study if the corticosteroid has efficacy in extending survival time.

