#### (1) Full analysis set (FAS)

The population of participants consisting of all enrolled patients after excluding (1) ineligible patients, (2) patients who were never exposed to the study drug (steroid or placebo) after allocation, and (3) patients for whom the data required for major assessments are not available

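### Survival time is assigned to a full analysis set whose entry depends on exposure and on data for undefined major assessments, so patients who die or deteriorate early can drop out of the survival comparison

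*Protocol*

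**What the plan says.** Survival time is item (3) of the efficacy endpoints in Protocol section 6.2.1: "Assess time to death with the day of enrollment (randomization) as the starting point. The efficacy is confirmed if the survival time is extended".

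Section 7.2 then fixes the analysis set: "The efficacy endpoint analyses are to be performed on the full analysis set (FAS"), with the per protocol set added for reference. Survival is given no set of its own.

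The FAS definition in 7.2 (1) starts from all enrolled patients and removes three groups: ineligible patients, "patients who were never exposed to the study drug (steroid or placebo) after allocation", and "patients for whom the data required for major assessments are not available". The protocol does not say which assessments are major. The only primary endpoint is the fatigue score of the questionnaire "used to evaluate QOL on Day 7 after study commencement" (section 6.1). Section 7.2 leaves details of handling missing and excluded cases to the statistical analysis plan, which is not at hand.

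**The concern.** A time-to-death analysis that starts at randomization should contain everyone randomized. Here the set is filtered by events after randomization: whether a dose was taken and, on the natural reading, whether a fatigue score was given about a week later. Dying, or becoming too ill to complete a form, is a main reason for having no score. Entry to the survival set is therefore partly decided by the outcome under study.

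Two things follow. Survival is overstated in both groups, because the removed patients are disproportionately those who die soonest. The comparison between groups is also no longer protected by randomization if early deaths or missing forms differ by group. Week 1 is the period of randomized treatment, and section 4.1 describes steroid treatment for the placebo group as delayed by about a week, so a difference in that week is of particular interest. The per protocol set gives no second view, because it is a subset of the FAS.

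**Working it through.** **Plan's own figures.** The protocol gives no figure for survival. Its sample size reproduces: for 0.5 SD, two-sided 5% and 90% power, 2 × (1.960 + 1.282)² / 0.5² = 84.06 per group, against 84 stated; 168 / (1 − 0.20) = 210. The dropout allowance is 210 − 168 = 42 patients. Section 4.2 names death, inability to complete the form and reduced cognition among its causes. If all 42 lacked the required data, 168 rather than 210 would enter the survival comparison.

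**Who lacks a post-baseline score.** The schedule in 4.15 has the questionnaire at baseline and at discontinuation or completion only, with nothing on Days 1 to 6. Sections 4.10.6 (4), 4.12.2 and 4.17.3 ask for assessments promptly at discontinuation and let data from the preceding 3 days stand in. A patient who stops treatment, completes the form and then dies can stay in the FAS. A patient who dies on treatment, or cannot complete the form, normally has no score. For that patient the only scheduled earlier form is the baseline one, which falls within 3 days only if treatment stops very early.

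**How many deaths by Day 7.** Section 3.1 takes end-stage as the last 1 to 2 months of life. Assume exponential survival with median m days (an assumption, not a protocol figure): P = 1 − 2^(−7/m).

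- m = 30: 14.9%, about 31 of 210
- m = 45: 10.2%, about 21 of 210
- m = 60: 7.8%, about 16 of 210

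**Effect on the survival estimate.** In the extreme case where every such death is removed, the median from randomization solves 2^(−(t − 7)/m) = 0.5, so t = m + 7. Medians of 30, 45 and 60 days become 37, 52 and 67.

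**Effect on the hazard ratio (HR).** Simulation with 20,000 patients per arm, exponential survival, censoring at 16 weeks and a Cox model, steroid versus placebo. Each cell gives the HR in all randomized patients → the HR after dropping all week-1 deaths.

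| True HR in week 1, then later | Median 4 weeks | Median 6 weeks | Median 8 weeks |
|---|---|---|---|
| 2, then 1 | 1.178 → 0.999 | 1.143 → 1.004 | 1.110 → 0.994 |
| 0.5, then 1 | 0.923 → 1.005 | 0.950 → 1.017 | 0.949 → 1.004 |
| 1 throughout | 1.012 → 1.017 | 0.992 → 0.994 | 0.995 → 0.994 |
| 0.8 throughout | 0.794 → 0.788 | 0.821 → 0.814 | 0.806 → 0.807 |

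The exclusion erases an effect confined to week 1, in either direction, and leaves a constant HR essentially as it was. The week-1 effects of 2 and 0.5 are illustrative; nothing in the protocol suggests them.

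**The case against.** The strongest reply is that the protocol never says the FAS requires a fatigue score. The analysis plan may define the required data endpoint by endpoint; for survival they would then be a date of death or last contact. That stands as a limit on certainty. It does not remove the point: section 7.2 itself assigns all efficacy endpoints to one FAS with one list of exclusions, and the exclusions for ineligibility and non-exposure reach survival on any reading.

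A reader might infer that every patient who dies in the treatment week is removed. The documents do not support that, because discontinuation forms and the 3-day rule can keep some of them in.

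A reader might also infer that an early harm would go unseen. It would not. Section 5.1 evaluates all adverse events during treatment, section 5.3 grades deaths related to adverse events, the safety set in 7.2 (3) needs only one dose, and serious events go to the independent data monitoring board. What is lost is their place in the survival comparison on which 6.2.1 rests an efficacy claim.

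Nor is it shown that the removed deaths are the only ones treatment could influence: effects of a one-week course need not end on Day 7, and 6.2.1 looks for an effect on survival as a whole.

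Finally, the death counts may be high. Patients must be able to swallow capsules and be free of delirium and apparent infection, so a constant hazard from Day 0 may overstate early deaths. At a 30-day median, 31 deaths would take 31/42 = 74% of a dropout allowance meant for five causes.

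**Conclusion.** The point holds in a conditional form. As written, section 7.2 sends a time-to-death endpoint counted from randomization to a set conditioned on later exposure and on data for undefined major assessments. If these mean the post-baseline fatigue score, patients who die or deteriorate before giving one leave the survival comparison. That inflates survival estimates and can mask or bias a difference arising in the treatment week.

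The size rests on assumptions: about 16 to 31 of 210 deaths by Day 7 under exponential survival with a median of 60 down to 30 days, of which an unknown share would be excluded. The HR shift appears when the treatment effect differs in week 1, or when missing forms differ by group in a way related to prognosis. It would be wrong to conclude that the survival HR is biased in general. The primary analysis, the sample size and the safety analysis are not touched.

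**What to change.** In section 7.2, state that survival time is analysed in all randomized patients, as randomized, from the day of enrollment, whether or not a dose was taken or any questionnaire exists. Keep the FAS for the questionnaire endpoints. Make the change before unblinding.

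Confirm as well that the outcome survey covers enrolled patients who never took a dose. Sections 4.1 and 4.16 (4) place the survey after the end of study treatment, 4.17.3 defines discontinuation as following at least one dose, and 4.9 ends the study for patients who cannot start without mentioning the survey. Section 15.1, by contrast, speaks of the deaths of all enrolled participants. It should not be assumed that these patients' death dates are already collected.

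The cost is one or two sentences and a little outcome follow-up for what should be few never-dosed patients. No change in patient numbers is needed.

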#### (1) Full analysis set (FAS)

The population of participants consisting of all enrolled patients after excluding (1) ineligible patients, (2) patients who were never exposed to the study drug (steroid or placebo) after allocation, and (3) patients for whom the data required for major assessments are not available

#### (2) Per protocol set (PPS)

The population of participants consisting of those in the FAS who were deemed protocol compliant with no protocol deviations

